# 11.3 Analysis Populations

#### 11.3.1 Intent-to-Treat Set

The Intent-to-Treat Set will include all subjects with at least one eye implanted with a study lens. Summaries and analyses of the ITT Set will classify subjects according to the treatment to which they were randomized.

#### 11.3.2 Safety Set

The Safety Set will include all subjects with at least one eye implanted with a study lens. Summaries and analyses of the Safety Set will classify subjects according to the treatment received.

#### 11.3.3 Per Protocol Set

The Per Protocol (PP) Set will include all bilaterally implanted subjects without major protocol deviations. Major protocol deviations are described in Section 11.5.7.

### 11.3.4 Patient Reported Outcome (PRO) Analytical Set

The PRO Analytical Set will include all subjects who submitted the preoperative questionnaires and at least one postoperative questionnaire.

# 11.4 Statistical Analysis

Summaries for continuous variables will include the sample size, mean, standard deviation, median, minimum, and maximum. Summaries for categorical variables will include the tabulation of frequencies and percentages.

Additional details will be provided in the statistical analysis plan (SAP), which will be completed and approved prior to database lock. Any changes to the plans in this clinical investigation plan will be noted in the SAP. Any changes to the analysis plans made after the SAP is approved may be documented using amendments to the SAP. Changes made after the last version of the SAP will be documented in the clinical study report.

If the Test IOL is statistically successful in all primary endpoints with success criteria, then the Test IOL will be statistically successful overall.

#### 11.4.1 Primary Safety Analyses

### 11.4.1.1 All Implanted Eyes with at Least One Serious Adverse Event

The proportion of all implanted Safety Set eyes with at least one serious adverse event will be summarized using categorical summary statistics by treatment received. Each eye will be counted only once in the calculation of the rate.

# 11.4.1.2 Secondary Surgical Interventions Related to the Optical Properties of the IOL

Secondary surgical interventions related to the optical properties of the IOL will be defined as IOL explantation, replacement, or repositioning due to subject intolerance of visual symptoms not adequately improved by spectacle correction. The investigators will apply this definition to classify each secondary surgical intervention as either related to the optical properties of the IOL or not related to the optical properties of the IOL.

Each eye will be classified as either having undergone a secondary surgical intervention related to the optical properties of the IOL or not having undergone such an intervention. Missing data will not be imputed. Secondary surgical interventions related to the optical properties of the IOL will be summarized categorically (Yes, No) by actual treatment received for Safety Set subjects in a table. Secondary surgical interventions will be further subcategorized and summarized categorically as Exchange, Removal, Repositioning, or Other.

#### 11.4.1.3 ISO Grid Adverse Events

Cumulative and persistent ISO grid AEs will be summarized categorically for all Test group eyes of the Safety Set by treatment. Subjects will be analyzed according to treatment received.

The numerator for each cumulative AE will be the number of all implanted Test group eyes reporting the AE at least once after surgery. The denominator for cumulative AEs will be the number of all implanted Test group eyes.

The numerator for each persistent AE will be the number of all implanted Test group eyes with the event at Visit 4 (Day 120 to Day 180 after second eye IOL implantation). The denominator for persistent AEs will be the number of all implanted Test group eyes present at Visit 4 (Day 120 to Day 180 after second eye IOL implantation).

For each ISO grid AE, a one-sided exact binomial test comparing the proportion of Test group eyes with the AE to the relevant control rate will be completed. If the resulting p-value is less than or equal to 0.05, then the null hypothesis will be rejected. If none of the null hypotheses are rejected, then the test lens will be statistically successful in these endpoints.

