Only subjects who are randomized but did not have the lens inserted into the eye at the first cataract surgery (Visit 00A) may be replaced. Subjects for whom the lens was inserted but not implanted will not be replaced. Subjects who successfully complete Visit 00A and do not successfully implant the assigned IOL at Visit 00B will continue participation for purposes of collecting safety information only for the "B" eye. Visual acuity measurements for a subject who does not implant the assigned IOL at Visit 00B will be only monocular for the "A" eye. A new subject number will be assigned for subject replacements, as long as the total number of treated subjects at the site does not exceed the maximum number specified in Section 5.3. Subjects who are discontinued from the study following treatment will not be replaced.

Discontinued subjects and discontinued subject eyes should be followed outside of the study protocol according to the Investigator's normal standard of care.

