# 10.4.5 Adverse Events at Subject Exit

Ongoing AEs will be followed until resolution, no further change in the condition is expected (i.e., event stabilized), or as dictated by standard of care. Documentation in the CRF of this follow-up is not required although subject care should continue as appropriate.

Ongoing SAEs and SADEs will be followed by the Sponsor and its representative(s) and the Investigator until the outcome is determined or until no further change in the condition is expected.

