	Day -30 to -5	Day 0	Day 1 to 2	Day 7 to 14	Day 30 to 60	Day 7 to 30	Day 1 to 2 Post Visit 00B	Day 7 to 14 Post Visit 00B	Day 30 to 60 Post Visit 00B	Day 120 to Day 180 Post Visit 00B
Binocular corrected distance contrast sensitivity testing (photopic with glare at 3, 6, 12 and 18 cpd) h										X
Binocular corrected distance contrast sensitivity (mesopic with and without glare at 1.5, 3, 6, and 12 cpd) h										X
Binocular CDVA Defocus Curves h										X
Intraocular Pressure	X		X	X	X		X	X	X	X
Slit-Lamp Exam	X		X	X	X		X	X	X	X
Pharmacologic Pupil Dilation j	X				X				X	$X^{\mathbf{k}}$
Dilated Fundus Exam	X				X				X	X k
Photography for rotational stability assessment 		X	X		X	X	X		X	X
Posterior capsulotomy assessment			X	X	X		X	X	X	X
Adverse Events	X	X	X	X	X	X	X	X	X	X
Concomitant Medications	X	X	X	X	X	X	X	X	X	X

- a Must occur before Operative Visit 00B
- b Review of inclusion/exclusion criteria prior to surgery
- c To additionally be completed at any post-operative Unscheduled Visit and prior to unscheduled study exit (e.g., IOL explanation).
- d Completed for both eyes. Also see footnote j.
- e Subjects will be randomized following determination of eligibility based on meeting all inclusion criteria and none of the exclusion criteria.
- f Distance to be 40 cm
- g Distance to be 66 cm
- h Conducted on a subset of subjects
-  Includes determination of medical and lens findings/complications, including decentration, tilt and PCO (note: lens findings/complications, including decentration, tilt and PCO evaluated post-operatively only).
- j Assessment for minimum pupil size of 5.0 mm in both eyes following pharmacologic pupil dilation with mydriatic agents is only performed at the pre-operative visit after all procedures listed in Appendix A prior to pharmacologic pupil dilation are completed.
- k If clinically indicated
-  Photograph are to be taken for all subjects to maintain masking of the assigned IOLs for subjects. Photographs will be sent to a central reading center for assessment of rotational stability for eyes implanted with trifocal IOLs. In addition, Investigators may elect to also take intraoperative photographs for placement of IOLs.

[figure not shown]

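### Implanted eyes that leave early stay in the cumulative safety denominators as event-free, with no rule to capture later events, so these rates can only err low

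*Combined protocol and SAP*

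**What the plan says.** All three primary safety variables (section 5.1.1) are defined through Visit 4, Day 120 to 180 after the second surgery.

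- **Cumulative ISO grid events (11.4.1.3).** Numerator: "The numerator for each cumulative AE will be the number of all implanted Test group eyes reporting the AE at least once after surgery". Denominator: "The denominator for cumulative AEs will be the number of all implanted Test group eyes".
- **Persistent grid events (11.4.1.3).** These are restricted: "The denominator for persistent AEs will be the number of all implanted Test group eyes present at Visit 4".
- **Serious adverse events (11.4.1.1).** The rate is over all implanted Safety Set eyes, each eye counted once.
- **Optical SSIs (11.4.1.2).** Every eye falls into one of two classes: it had such an operation, "or not having undergone such an intervention. Missing data will not be imputed". The Synopsis takes this summary over all Safety Set eyes.
- **After discontinuation (6.3.4).** "Discontinued subjects and discontinued subject eyes should be followed outside of the study protocol", under the Investigator's usual care.
- **Events ongoing at exit (10.4.5).** They are followed to resolution or stability, but for non-serious events "Documentation in the CRF of this follow-up is not required although subject care should continue as appropriate".
- **Explantation (Appendix A, footnote c).** It asks for an assessment "prior to unscheduled study exit (e.g., IOL explanation"). The discontinuation reasons in 6.3.4, an open list, do not mention explantation.

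**The concern.** A cumulative rate through Visit 4 needs each eye in the denominator to be observed through Visit 4, or censored when observation stops. Here the denominator is fixed at implantation, while the routine for collecting new events stops at exit. The optical-SSI classification has two classes and no category for unknown status. The persistent-event rate allows for absence at Visit 4; the cumulative rates do not.

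The error has one direction: an event that is not collected can only lower the rate. In section 11.4.1.3 the Test lens succeeds if no null hypothesis is rejected, so undercounting helps it pass. For optical SSIs the missing eyes may be the relevant ones. Section 10.3 accepts that explantation may be needed when optical side effects are intolerable, and section 7.2 says that individual unmasking normally leads to withdrawal.

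**Working it through.** **1. The plan's own figures.** Section 11.2.3: 100/(1 − 0.1) = 111.1, rounded up to 112 Test subjects; 50/(1 − 0.1) = 55.6, rounded up to 56 Control subjects; total 168. The Synopsis gives 224 Test and 112 Control eyes enrolled, with 200 and 100 completing. These figures reproduce.

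**2. Eyes at issue.** Test: 224 − 200 = 24 eyes, a share w = 24/224 = 0.107. Control: 112 − 100 = 12 eyes, and 12/112 is the same share. These are upper figures, because they treat all loss as bilateral and after implantation. A subject never implanted is outside the Safety Set, and one who exits between surgeries contributes one eye.

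**3. Size of the understatement.** Let R be the risk in exiting eyes relative to completing eyes, and f the share of the exiting eyes' risk through Visit 4 that falls after exit and is not captured. Then

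relative understatement = w·R·f / [(1 − w) + w·R].

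With R = 1 this reduces to w·f. For R = 2 and f = 1 it is 0.2143/(0.8929 + 0.2143) = 19.4%.

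| R | f = 0.25 | f = 0.5 | f = 0.75 | f = 1 |
|---|---|---|---|---|
| 1 | 2.7% | 5.4% | 8.0% | 10.7% |
| 2 (assumed) | – | 9.7% | – | 19.4% |
| 3 (assumed) | – | 13.2% | – | 26.5% |
| 5 (assumed) | – | 18.8% | – | 37.5% |

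The column f = 1 is an extreme: it means exit straight after surgery and nothing learned later.

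**4. In counts.** Two recorded optical SSIs give 2/224 = 0.89%. If the 24 exiting eyes contributed no observation, the rate over observed eyes is 2/200 = 1.00%. One missed bilateral case would move 0/224 to 2/224 = 0.89%.

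**5. Effect on a grid test.** The ISO grid rates are not in the documents, so the values below are assumptions. The test is the plan's one-sided exact binomial at 0.05 with n = 224, eyes taken as independent as the plan assumes, and a true rate of twice the grid rate. With R = 1 the recorded rate is the true rate times (1 − w·f).

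| Assumed grid rate | Smallest rejecting count | Chance of flagging, full capture | f = 0.5 | f = 1 |
|---|---|---|---|---|
| 0.3% | 3 | 15% | 14% | 12% |
| 1% | 6 | 29% | 25% | 21% |
| 3% | 12 | 70% | 62% | 54% |
| 5% | 18 | 86% | 80% | 71% |

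**The case against.** The strongest reply is that non-capture is inferred from silence. Section 10.4.2 requires events during the investigation to be entered and sets no cut-off at a subject's exit. Device-related serious events must go to Health Canada within 72 hours of discovery (10.4.4.1, 10.4.4.3), with no stated limit to active participants. Discontinued subjects stay under the Investigator's usual care. This stands in part: a reader might infer that later events are never recorded, and the documents do not support that. They leave capture to chance, which is a risk and not a certainty.

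Other tempting readings also go too far:

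- **Section 10.4.5 as a source of lost events.** Its relief from case report form (CRF) entry concerns follow-up of events already ongoing at exit, which are already in the cumulative numerator.
- **Explantations escaping the count.** Footnote c asks for an assessment before exit, so an explantation that triggers exit is known and is counted if optical. The serious-event rate counts each eye once, so later complications of an eye already counted do not change it; only other grid lines could be affected.
- **Unknown status necessarily scored No.** The no-imputation sentence in 11.4.1.2 could also mean that such eyes are left out. The text does not settle this for optical SSIs. For cumulative grid events the denominator is explicit.

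The plan also limits the problem. Section 6.3.4 asks for a final visit before discontinuation. Section 6.3.5 requires repeated contact attempts and a certified letter, and aims for loss below 10%. Subjects who miss visits remain in the study (6.3.3), and a discontinued second eye stays in safety follow-up (6.3.4, 9.1.3). Section 11.4.5 tabulates discontinuations by stage and reason. These measures reduce the number of exits and secure events up to exit; they do not reach a new event after it.

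Two points stay open. If the ISO historical rates were themselves computed over all implanted eyes with similar loss, the comparison would be closer to like with like; the documents do not say. Section 11.4 defers detail to a statistical analysis plan, which could add the analysis but could not recover status that was never collected.

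**Conclusion.** The point holds as a modest, one-directional weakness. The cumulative primary safety rates treat an event-free exit as event-free through Visit 4, and no section requires later events to be sought. Under equal risk the understatement is at most about 10.7% relative, if all 24 planned lost Test eyes are bilateral, implanted and unobserved. It is about half that if half of their risk falls after exit.

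A reader might infer a much larger bias by giving exiting eyes a high SSI rate, or by crediting them with no events even before exit. Neither is supported: the documents give no rate for exiting eyes, and events before exit are collected. The larger values in the table rest on the assumption that exit is linked to visual intolerance.

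The serious-event and optical-SSI rates carry no hypothesis (11.1.1.1, 11.1.1.2), so only the cumulative grid tests face a formal decision. There undercounting favours success, and the loss of sensitivity depends on grid rates that the documents do not state.

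**What to change.** - **Sections 6.3.4 and 10.4.5.** State that, for subjects with an implanted study lens who stop attending, SSI, serious-event and grid-event status through the Visit 4 window will be sought by telephone or chart review and entered in the CRF, unless consent for this is withdrawn.
- **Sections 11.4.1.1 to 11.4.1.3.** Keep the all-implanted rate. Beside it report a Kaplan-Meier cumulative rate, or a rate over eyes that had an event or have known status through Visit 4, with the number and timing of early-exit eyes. Do not use completers alone as the denominator while keeping pre-exit events in the numerator; that errs upward. Kaplan-Meier assumes that exit is unrelated to risk, so it supplements the status check and does not replace it.
- **Section 11.4.1.2.** Say how an eye of unknown status is classified.
- **Appendix A, footnote c, and section 6.3.4.** Reconcile whether explantation ends study participation; section 11.4.7 speaks only of exclusion from the Per Protocol Set.

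The cost is protocol wording, one status form, one extra table and a check for about 17 to 18 subjects (10% of 168 = 16.8; 168 − 150 = 18). The reported rates may become slightly less favourable. The capture rule should be set prospectively, because status not collected during the study may be hard to recover.

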#### 11.4.2 Secondary Safety Analyses

### 11.4.2.1 Subjects Experiencing at Least One Severe Visual Disturbance

The incidence of Safety Set subjects experiencing at least one severe visual disturbance, defined as the highest grade of severity or bothersomeness (separately) reported by subjects using the Quality of Vision (QoV) questionnaire through Post-Operative Visit 4 (Day 120 to Day 180 after second eye IOL implantation), will be summarized using descriptive statistics by treatment.

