## 5.1.1 Safety Variables

The primary safety variables will be:

- The incidence of all serious adverse events, including secondary surgical interventions (SSIs) related to the optical properties of the IOL, through Post-Operative Visit 4 (Day 120 to Day 180 after second eye IOL implantation)
- The cumulative rate of secondary surgical interventions due to the optical properties of the lens, through Post-Operative Visit 4 (Day 120 to Day 180 after second eye IOL implantation)
- The incidence of adverse events, through Post-Operative Visit 4 (Day 120 to Day 180 after second eye IOL implantation), compared to ISO Safety and Performance Endpoint (SPE) rates as defined in ISO 11979-7:2018 Annex E

The secondary safety variables will be:

(Data for these safety variables will be summarized with descriptive statistics lacking hypothesis)

- The incidence of subjects experiencing at least one severe visual disturbance, defined as the highest grade of severity or bothersomeness (separately) reported by subjects using the Quality of Vision (QoV) questionnaire through Post-Operative Visit 4 (Day 120 to Day 180 after second eye IOL implantation)
- Photopic contrast sensitivity with glare at Post-Operative Visit 4 (Day 120 to Day 180 after second eye IOL implantation)
- Mesopic contrast sensitivity with glare at Post-Operative Visit 4 (Day 120 to Day 180 after second eye IOL implantation)
- Mesopic contrast sensitivity without glare at Post-Operative Visit 4 (Day 120 to Day 180 after second eye IOL implantation)

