#### 10.3 Risk Assessment, Risk Mitigation, and Anticipated Benefit

The model MX60EFH IOL has similar material, mechanical, and biocompatibility properties to the FDA-approved model MX60 and optically equivalent MX60E monofocal IOLs that have

been shown to be safe for implantation in humans.  Reduced contrast sensitivity and increased visual disturbances, such as glare and halo, are known to occur more frequently with multifocal IOLs and will be evaluated in this study through the patient reported outcome (PRO) Quality of Vision questionnaire and a contrast sensitivity sub-study.

The known risks of multifocal IOL implantation that exist in addition to the risks of monofocal IOLs include the following:

- Under scotopic and mesopic conditions, the patient has reduced contrast sensitivity,
- There is an increased risk of post-operative photic effects such as halos and glare.

Studies on other adverse perception effects following multifocal IOL implantation, such as stereo acuity disturbances and aniseikonia, have generally indicated an acceptable performance range. 

Multifocal IOLs achieve correction of presbyopia by dividing incoming light into two or more focal points. Patient selection and counselling are particularly important with these IOLs. There may be a symptomatic reduction in the quality of distance vision, particularly if other ocular pathology is present. Therefore, the candidacy of patients with amblyopia or abnormalities of the cornea, optic disc, and macula for a multifocal IOL must be carefully considered. Although uncommon, explantation of multifocal IOLs may become necessary if optical side effects are intolerable. 

A Cochrane systematic review concluded that multifocal IOLs are effective at improving near vision relative to monofocal IOLs, although there is uncertainty as to the size of the effect. Whether that improvement outweighs the adverse effects of multifocal IOLs, such as glare and haloes, will vary between people. Motivation to achieve spectacle independence is likely to be a deciding factor. 

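### The Quality of Vision analysis described in the protocol counts only top-grade symptoms pooled over all items, so it cannot reflect a rise in mild or moderate glare or halos

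*Combined protocol and SAP*

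**What the plan says.** Section 10.3 says of visual disturbances, glare and halo among them: "known to occur more frequently with multifocal IOLs and will be evaluated in this study through the patient reported outcome (PRO) Quality of Vision questionnaire", alongside a contrast sensitivity sub-study. It lists two risks that multifocal lenses add to those of monofocal lenses: "Under scotopic and mesopic conditions, the patient has reduced contrast sensitivity", and "There is an increased risk of post-operative photic effects such as halos and glare". The first has its own sub-study (11.2.2.2) and analysis (11.4.2.2). For the second, the QoV questionnaire is the named instrument.

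Section 11.4.2.1 then describes one analysis: the proportion of subjects in the Safety Set "experiencing at least one severe visual disturbance, defined as the highest grade of severity or bothersomeness (separately) reported by subjects" on the QoV through Visit 4. The result "will be summarized using descriptive statistics by treatment". The Synopsis and sections 5.1.1 and 10.1 define the same variable. Section 5.1.1 says of the secondary safety variables: "Data for these safety variables will be summarized with descriptive statistics lacking hypothesis".

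The flow chart in Appendix A schedules the questionnaires preoperatively and at Visit 4. Section 11.3.4 defines a Patient Reported Outcome Analytical Set and section 11.4.5 counts it, but no analysis in section 11.4 uses it. Section 11.4 leaves further detail to a statistical analysis plan due before database lock. No separate text of that plan is in the supplied document.

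**The concern.** The questionnaire records grades, and the described summary uses only the highest one. It also merges all symptoms, so a top grade on any item counts the same as a top-grade halo. A subject who moves from no halo to a mild one, or from mild to moderate, contributes nothing.

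Similar severe-disturbance rates in the two arms could therefore be read as no added disturbance when the grades already collected would show a clear shift. The trial would then answer only part of the question that section 10.3 sets for this questionnaire.

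**Working it through.** **1. The plan's own figures.** Section 11.2.3: 100/(1 − 0.1) = 111.1, rounded up to 112 Test subjects; 50/(1 − 0.1) = 55.6, rounded up to 56 Control subjects; 112 + 56 = 168. This reproduces. It rests on the acuity endpoints, and the documents give no sample size, rate or hypothesis for the QoV. I use the 100 and 50 completers below.

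**2. What the definition can and cannot register.** Let G(i,s) be the grade that subject i gives symptom s, with K the highest grade. The planned variable is Y(i) = 1 if G(i,s) = K for at least one s, and 0 otherwise. It is formed once for severity and once for bothersomeness. Any change among grades below K leaves Y(i) unchanged, and Y(i) = 1 does not say which symptom was responsible. This step needs no assumption about the instrument.

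**3. Whether another described analysis fills the gap.** Sections 11.4.1.1 to 11.4.1.3 cover serious adverse events, secondary surgery for optical reasons, and ISO grid events in Test eyes against historical rates. Increased glare or halos is in the anticipated adverse event list of section 10.4.1, without the asterisk that sets a reporting threshold, so milder cases can be recorded. No by-arm table of non-serious events outside the ISO grid is described.

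**4. Illustration of the information lost.** Assumptions: one symptom with four grades (none/mild/moderate/top), 100 Test and 50 Control subjects, two-sided 5%, 4,000 simulated trials per scenario. Fisher's test on the top grade is compared with the Mann-Whitney test on all grades. The tests are a yardstick only.

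| Scenario | Control % | Test % | Mild + moderate | Top-grade cut | All grades |
|---|---|---|---|---|---|
| A | 60/25/12/3 | 30/40/27/3 | 37 to 67 (+30) | 2.6% | 91% |
| B | 60/25/12/3 | 45/32/20/3 | 37 to 52 (+15) | 2.1% | 40% |
| C | 80/14/5/1 | 55/28/16/1 | 19 to 44 (+25) | 0.6% | 87% |
| D | 60/25/12/3 | 30/38/26/6 | 37 to 64 (+27) | 3.6% | 94% |

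In A to C the top-grade rate is equal in the two arms, so that column is only the false-positive rate of Fisher's test. Repeat runs of A gave 2 to 3% against 91 to 92%.

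For A, the Mann-Whitney probability that a Test subject has the worse grade (ties counted half) is 0.60 × 0.85 + 0.25 × 0.50 + 0.12 × 0.165 + 0.03 × 0.015 = 0.655, against 0.5 for no difference.

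**5. Precision of the planned contrast.** The 95% half-width for a difference in one top-grade rate is 1.96 × √[p(1 − p)(1/50 + 1/100)]. At p = 3% this is 1.96 × √(0.0291 × 0.03) = 5.8 points; at 10% it is 10.2 points.

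**6. When the top grade shifts too.** Assume a Control top-grade rate of 5% and a proportional-odds shift with odds ratio 2. The Control odds are 0.05/0.95 = 0.0526; doubled, 0.1053, which is a Test rate of 9.5%. For one symptom, the top-grade cut detects this in about 8 to 9% of trials and the full scale in about 40 to 60%, depending on the lower grades.

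The planned endpoint pools symptoms, however. With eight symptoms assumed, correlated at 0.3 to 0.5, the pooled Control rate is about 22 to 27%. The pooled top-grade endpoint then detects:

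- odds ratio 2: about 37 to 48% of trials if all eight symptoms shift, about 7 to 8% if only two do;
- odds ratio 3: about 81 to 90% if all eight shift, about 15 to 19% if only two do.

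One symptom on the full scale, in a comparable run, gave about 58% and 93% at these odds ratios.

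**The case against.** The strongest objection concerns size. The endpoint pools symptoms, so it need not be rare. If the lens worsened every symptom across the whole scale, the severe-disturbance table would show much of it, and the gap to an ordinal analysis would be modest. This stands. A reader might take the one-symptom figures (about 9% against 60%) as the loss on the planned endpoint. The documents do not support that, because they give neither the number of items nor the grades, and the result turns on how many symptoms shift.

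A reader might also infer that graded QoV tables are excluded altogether. Section 11.4 defers detail to a later analysis plan, the supportive acuity variables have no subsection of their own there, and the unused Patient Reported Outcome set suggests that more may be intended. This also stands: the text supports only that this is the one QoV analysis described. Even so, nothing supplied commits to a table of grades.

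A third objection is that the variable is purely descriptive and that severe disturbance matters most to patients. Both are true. Neither is a reason to discard the lower grades, since a descriptive table has no power constraint, and section 11.4 already summarises categorical variables by frequencies and percentages. The severe-disturbance summary would remain.

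**Conclusion.** The concern holds in a limited form. The one QoV analysis described is insensitive by definition to changes below the top grade and does not identify glare or halos, although section 10.3 gives this questionnaire the task of evaluating them. That part needs no assumption.

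The size does. With a four-grade symptom, 100 v 50 subjects, the top grade fixed at 3% and mild-to-moderate symptoms up 30 points, the top-grade cut flags about 3% of trials against about 92% on the full scale. If the top grade rises on all symptoms, the pooled endpoint loses much less; if only two of eight assumed symptoms shift, it detects little.

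Two stronger readings should be avoided. One is that added glare or halo would go unseen in the trial. Milder cases can be reported as adverse events, and symptoms leading to explantation, replacement or repositioning fall under a primary safety endpoint. The other is that photic effects are the main added risk; section 10.3 lists them as one of two and does not rank them. No primary conclusion depends on this point. It is a low-cost improvement.

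**What to change.** Keep the severe-disturbance incidence in section 11.4.2.1. Add there, or in the statistical analysis plan before database lock:

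- a table of every grade for each QoV symptom, separately for severity and bothersomeness, by treatment received, preoperatively and at Visit 4, with the analysis set stated;
- glare and halos named as the symptoms of main interest;
- for these, a Test-versus-Control ordinal estimate at Visit 4 with a 95% interval, for example the Mann-Whitney probability or a common odds ratio, labelled supportive.

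The choice of ordinal measure is secondary; the grade-by-symptom table does most of the work. The cost is a few lines of text and one more output from data already collected, with no extra visits or subjects. The downside is more safety estimates without multiplicity control, which the supportive label should make plain.
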